3.3 Randomization and double- blinded study

Patients were allocated randomly to SAPB & ESPB group and PVB group according to computer-generated random number table. All patients and an investigator who was responsible for follow-up during 48 postoperative hours were blinded to the randomization groups. The investigator instructed the patients to use a patient-controlled intravenous analgesia (PCA) device for postoperative pain management, the visual analog scale to assess pain at rest and during coughing, and the correct use of a pulmonary function meter.

Serratus anterior plane block combined with erector spinae plane block were performed in the experimental group after anesthesia, while thoracic paravertebral nerve block was performed in the control group .

4 Subject selection and withdrawal

4.1 Inclusion criteria:

1. American Society of Anesthesiologists (ASA) physical status I-II
2. Age from 18–75 years
3. BMI 19–28 kg/m²;
4. Selective thoracoscopic partial pneumonectomy under general anesthesia;
5. Informed consent has been signed.

4.2 Exclusion criteria:

1. Daily use of opioid analgesics or history of opioid abuse
2. Reoperation in ipsilateral thorax
3. Allergic to any of the drugs used in the study, or have a history of drug allergy
4. Have mental or nervous system diseases, motor or sensory defects;
5. Coagulation dysfunction
6. Have cognitive dysfunction, unable to cooperate with the research;
7. Severe renal, liver or heart dysfunction
8. Chest wall and spine trauma, infection, deformity and other conditions where nerve block cannot be carried out
9. Participated in other clinical trials within 3 months prior to study inclusion
10. Other reasons considered unsuitable for clinical trials by the investigator
11. Refusal to participate.

4.3 Exit criteria:

1. Conversion to thoracotomy unrelated to anesthesia;
2. The operation lasted more than 4 hours;
3. The consciousness in PACU was completely awake, and there was no effect in plane block;
4. Serious adverse events, complications or special physiological changes are not suitable for further study;
5. The patient or his/her guardian requests to withdraw;
6. Other researchers cited reasons to stop the study

5 Research process

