The anesthesiologist went to the ward one day before the operation to evaluate the anesthesia of the patients who were going to undergo thoracoscopic pulmonary resection, signed the informed consent form, and selected the subjects according to the inclusion criteria and exclusion criteria. They were randomly divided into SAPB & ESPB group(test group) and PVB group(control group). Patients were also taught how to use the spirometer, patient-controlled intravenous analgesia(PCA), and visual analogue scale (VAS). (VAS: a 100 mm horizontal line, with 0 mm at one end of the line, indicating no pain. The other end is 100mm, indicating severe pain. The middle portion indicates varying degrees of pain.)

- 1) All patients were forbidden to drink and eat before operation without preoperative medication
- 2) After the patients entered the operating room, the investigator measured the

VAS score of the patient at rest and coughing in the sitting position. FVC (L), FEV₁ (L) and FEF 25% -75% (L/sec) were measured by spirometer for three times. Patients were assessed preoperatively using the QoR-15 Patient Questionnaire (see attached page).

- 3) Blood pressure, pulse, oxygen saturation and ECG were monitored. Anesthesia induction was performed after mask oxygenation: parecoxib sodium 40 mg, penehyclidine hydrochloride 0.5 mg, tropisetron 2 mg and sufentanil 0.5 μ g \cdot kg $^{-1}$, propofol 1.5–2.0 mg \cdot kg $^{-1}$ and rocuronium 0.8 mg \cdot kg $^{-1}$.
- 4) Performing tracheal intubation, ultrasound-guided radial artery cannulation to monitor ambulatory blood pressure and internal jugular central venous catheterization to establish a central venous channel.
- 5) Ultrasound-guided serratus anterior plane block combined with erector spinae plane block was performed in the experimental group. The erector spinae plane block was performed at T5 and T7 segments, with 10 ml 0.4% ropivacaine in each segment and 20 ml 0.4% ropivacaine in serratus anterior plane block. The control group received ultrasound-guided thoracic paravertebral block at T5 and T7 with 20 ml of 0.4% ropivacaine in each segment.

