- 6) Anesthesia maintenance: 1-2% sevoflurane, dexmedetomidine 0.5 μ g \cdot kg $^{-1}$ \cdot h $^{-1}$ and remifentanil 0.1-0.2 μ g \cdot kg $^{-1}$ \cdot min $^{-1}$. Maintain the stability of intraoperative vital signs. Volume control ventilation mode: tidal volume was 6-8ml/kg, airway pressure was maintained within 25cmH₂O, end-expiratory CO₂ was maintained within 35-45mmHg, and lungs were dilated once every 1 hour. ECG, HR, BP, SpO₂, PetCO₂, body temperature, liquid intake and output were monitored. During the operation, vasoactive drugs were used as needed to maintain blood pressure, heart rate was maintained within \pm 20% of the preoperative basic level. Correct acid-base imbalance and electrolyte disturbance according to arterial blood gas analysis.
- 7) analgesic connection: intravenous injection of 5mg oxycodone 30 minutes before the end of surgery.
- 8) At the end of the operation, the endotracheal tube was removed when the patient was awake. Measure the level of nerve block when the patient is conscious. If there was no nerve block plane, the patient was withdrawn from the trial. The patient-controlled intravenous analgesia, which equipped with 0.5mg/ml oxycodone, 1ml/h background infusion, 3ml additional infusion and locked for 5min, was used immediately after extubation.
- 9) The patients were observed in the PACU for one hour, and the PCA could be applied for additional analgesia according to the needs of the patients. The patient was given rescue analgesia, a single intravenous dose of 2 mg of oxycodone, if the pain was not relieved or the patient requested it. Patients took a sitting position and measured the VAS scores of the patients at rest and coughing at 1h postoperatively. FVC (L), FEV₁ (L) and FEF 25% -75% (L/sec) were measured by spirometer for three times., and three indexes of FVC (L), FEV₁ (L) and FEF 25% -75% (L/sec) were recorded by spirometer for three times. Ask the patient if there are any adverse reactions, such as nausea, vomiting, itching, dizziness, headache, shoulder pain, respiratory depression, etc.

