10) After returning to the ward, the patient can press the PCA for additional analgesia according to the needs. The patient was given rescue analgesia, a single use of diclofenac sodium suppository, if the pain was not relieved or the patient requested it. Investigators conducted postoperative visits at 2h, 4h, 8h and 24h postoperatively, the dosage of PCA, the times of rescue analgesia, VAS scores at rest and cough and adverse reactions were recorded. FVC (L), FEV1 (L) and FEF 25% -75% (L/sec) were recorded for three times by spirometer in the sitting position at 4h and 24h postoperatively. Patients were assessed postoperatively using the QoR-15 Patient Questionnaire at 24h postoperatively.

6. Outcome measurements

6.1 The primary outcome :

Cumulative morphine consumption at 24h postoperatively

6.2 The secondary outcomes:

- (1) The cumulative morphine consumption at 1h, 2h, 4h and 8h postoperatively.
- (2) The times of remedial analgesia at 1h, 2h, 4h, 8h and 24h postoperatively.
- (3) VAS score at rest and cough at 1h, 2h, 4h, 8h and 24h postoperatively.
- (4) The changes of FVC (L), FEV₁ (L) and FEF 25% - 75% (L / sec) were observed before operation, 1h, 4h and 24h after postoperatively.
- (5) Changes of QoR-15 questionnaire scores before and 24h postoperatively.
- (6) Postoperative complications and rehabilitation time nodes (including drainage tube removal time, discharge time, etc.).

7 Security

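### Patients with no detectable block are withdrawn after randomisation, and the plan neither keeps their 24h data nor names an analysis set

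*Combined protocol and SAP*

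**What the plan says.** Section 5 places allocation at the visit one day before the operation: "They were randomly divided into SAPB & ESPB group(test group) and PVB group(control group". The block follows induction (step 5). Its level is checked once the patient is conscious after extubation, and step 8 says: "If there was no nerve block plane, the patient was withdrawn from the trial". Section 4.3, item 3 states the matching exit criterion: "The consciousness in PACU was completely awake, and there was no effect in plane block". PCA starts immediately after extubation (step 8), and the primary outcome is cumulative consumption at 24h (Section 6.1).

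Two other exit criteria also act after randomisation: "Conversion to thoracotomy unrelated to anesthesia" (item 1) and "The operation lasted more than 4 hours" (item 2).

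On what happens to these patients' data:
- Section 9.1 classes anyone who does not complete the observation cycle as a dropout.
- Sections 9.2 and 9.3 require reasons and certain notifications, but say nothing about outcome data.
- Section 7.1 continues follow-up for adverse events only.
- Section 10 lists tests. It offers a t-test or Mann-Whitney test for measurement data, and names morphine consumption among the data for one-way ANOVA. It gives no analysis set, no missing-data rule and no statement of one- or two-sided testing. A one-sided test is mentioned only in Section 3.2.

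**The concern.** Whether a block is detectable at emergence is a result of the technique to which the patient was assigned. Removing patients on that result, after randomisation and before the outcome has accrued, means that the groups compared are no longer the groups randomised.

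The trial asks whether the combined plane blocks can replace the paravertebral block. Complete failure of a technique bears directly on that question. It is not a planned outcome by arm in Section 6, and if failed blocks are left out it does not reach the primary outcome either. Consumption that was never collected cannot be recovered at the analysis stage, so the matter needs settling before enrolment.

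**Working it through.** **1. Reproduce the plan's sample size.** Inputs from Section 3.2: pilot SDs 4.8 and 4.2 mg, difference 2.5 mg, one-sided 0.05, power 80%, dropout 10%.
- Pooled SD = sqrt((4.8² + 4.2²)/2) = 4.51 mg.
- n per group = 2 × (4.51 × (1.645 + 0.842)/2.5)² = 40.2, so 41. This matches.
- 82/0.90 = 91.1, so 92 in total, or 46 per group. This matches.

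Raising 41 to 46 fits an analysis without the dropouts, but the text does not say so.

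**2. Bias if failed blocks are left out.** Let f be the complete-failure rate in an arm, and D the extra 24h opioid of a failed block over a detectable one in that arm. The mean over all randomised in an arm is the detectable-block mean plus f × D. Taking benefit as control minus test:

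benefit among detectable blocks − benefit among all randomised = fT × DT − fC × DC.

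A positive value favours the test arm and a negative value favours control. It is zero if f × D is equal in the two arms. The documents give neither f nor D.

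**3. A scale for D.** The PCA setting is "0.5mg/ml oxycodone, 1ml/h background infusion, 3ml additional infusion and locked for 5min". The background alone is 0.5 × 1 × 24 = 12 mg. Counted 1:1 (an assumption, since no morphine conversion is given), the pilot means leave 23.7 − 12 = 11.7 mg and 28.7 − 12 = 16.7 mg for everything else. An excess of 5 mg is then a 30–43% rise in that part (5/16.7 and 5/11.7), and 10 mg a 60–85% rise. So 10 mg is large. Ward rescue is "a single use of diclofenac sodium suppository", a non-opioid, which would tend to make D smaller.

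**4. Effect on error rates (illustration only).** Assumptions: 41 analysed per group, SD 4.51 mg, no true difference among all randomised, equal D in both arms. Standard error = 4.51 × sqrt(2/41) = 0.996 mg. Error is read from the noncentral t with 80 df and noncentrality bias/0.996, with critical values 1.990 (two-sided) and 1.664 (one-sided).

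| Bias (mg) | Example gap in failure rate | Two-sided error | One-sided, bias favours test | One-sided, bias favours control |
|---|---|---|---|---|
| 0 | none | 5.0% | 5.0% | 5.0% |
| 0.1 | 2 points at 5 mg | 5.1% | 6.1% | 4.1% |
| 0.25 | 5 points at 5 mg | 5.7% | 8.1% | 2.9% |
| 0.5 | 5 points at 10 mg | 7.9% | 12.6% | 1.6% |
| 1.0 | 10 points at 10 mg | 16.8% | 25.8% | 0.4% |

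If the bias favours control, the cost is power. For a true 2.5 mg, one-sided power falls from 80% to 77%, 72%, 64% and 44% at the four non-zero biases.

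**5. Power if these patients are kept.** With 46 analysed per group and a t-test for 2.5 mg, one-sided power is 80% at an SD of about 4.78 mg (6% above 4.51) and 77% at SD 5.0. The two-sided powers are about 70% and 66%. Retained block failures alone give SD = sqrt(4.51² + f(1 − f)D²). With 5% failing in both arms this is 4.64 mg at D = 5 and 5.01 mg at D = 10, with one-sided power of 82% and 77%.

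**The case against.** The strongest reply is that no material bias has been shown. Without f or D nothing can be, and a comparison among working blocks is a recognisable, if narrower, aim. Section 2 asks only whether the combined block gives adequate analgesia. That is fair as to size. It does not close the gap, because the plan does not say which comparison it wants, and following its withdrawal rule gives the narrower one by default.

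A second reply concerns the test. One-sided testing appears only in the sample-size paragraph. Section 10 names ANOVA for morphine consumption, and with two groups at one time point that is equivalent to a two-sided t-test. This stands, so the two-sided figures come first. On that scale the distortion is small for gaps up to 5 points at 5 mg. Retained failures may also skew the data and move the analysis to Mann-Whitney, which the t-test figures do not model.

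Three stronger readings are tempting, and the documents do not support them:
- **That item 3 removes failures from the test arm only.** It says plane block, words otherwise found in the names of the test-arm techniques, while the control technique is described differently: "The control group received ultrasound-guided thoracic paravertebral block at T5 and T7". But step 8 describes the same check with no restriction by arm. This is a wording mismatch to reconcile, not evidence of one-directional removal.
- **That failure counts will be lost.** Section 9.3 lists no block-failure category, but it requires a reason for every dropout and includes a residual category, and step 8 has the block level measured. Counts should be recoverable. What is missing is a plan to report them by arm, and the 24h data.
- **That the exclusion favours the test arm.** The sign depends on which arm has the larger f × D, and nothing in the documents settles that.

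**Conclusion.** The point holds as a gap in the plan that should be fixed. Withdrawal on block failure after randomisation is explicit, and so is the absence of a data-retention rule or a named analysis set. That these patients go unanalysed is an inference, supported by the dropout definition in Section 9.1 and the inflation from 41 to 46 per group. A reader might take it as stated policy, but it is not.

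The bias has unknown sign and size and could be zero. On the assumed values it is slight at 5 mg per failure (two-sided error 5.1% to 5.7%) and matters only with a large excess of 10 mg (7.9% to 16.8%). The one-sided figures apply only if the final test is one-sided. Confidence is medium.

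**What to change.** Change data collection and analysis only, with no change to care:
- Record absence of a block plane as an event, not as a reason to stop data collection.
- Collect 24h opioid consumption and the scheduled visit data on every randomised patient who had surgery and has not withdrawn consent to data collection, including those meeting exit criteria 1 to 3.
- Make the primary analysis all such patients by assigned group.
- Report complete block failure by arm, and the number of missing 24h values by arm with reasons.
- Keep the detectable-block comparison as a sensitivity analysis.
- Reconcile the wording of Section 4.3, item 3 with Section 5, step 8 so that both plainly cover the same patients.
- State whether the final test is one-sided or two-sided.

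The cost is protocol and SAP wording, plus visits through 24h for at most about 9 patients (10% of 92) if the dropout allowance is right. That is an upper figure, because the allowance also covers consent withdrawals. The statistical price is somewhat more variance, partly offset by analysing up to 46 rather than 41 per group.

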Clinical study protocol

Program name: Ultrasound-guided serratus anterior plane block combined with erector spinae plane block versus thoracic paravertebral block for postoperative analgesic effect and recovery after thoracoscopic surgery

NCT number: 1000012129

Date of applicant: August 29, 2022

1. Research Background and Significance:

Thoracoscopic surgery is becoming increasingly popular because it has several advantages compared with thoracotomy of small incision, fast postoperative recovery, fewer perioperative complications, short hospital stay, and improved postoperative quality of life.^[1] However, patients are still faced with moderate to severe pain after thoracoscopic surgery. How to control pain effectively and promote postoperative recovery is still a challenging problem.^[2-3]

Opioids usage, epidural analgesia, thoracic paravertebral block, intercostal nerve block, erector spinal plane nerve block, and serratus anterior plane block are commonly used to control pain after thoracoscopic surgery. Although the use of opioid analgesics can effectively control pain, with the increase of the dose of opioids, the adverse effects will become more pronounced, such as respiratory depression, which is not conducive to the postoperative recovery. Regional anesthesia techniques are more effective in relieving pain than opioids alone and can reduce opioid dosage, thus helping to reduce opioid-related adverse effects.^[4] Epidural analgesia was once considered as the gold standard for post-thoracotomy pain control,^[5] but it is not widely used for pain management after thoracoscopic surgery because it is related to high potential risks of nerve lesions, rupture of spinal dura mater, epidural hematoma, hypotension and difficult to operate for the inexperienced.

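### Minor: the only stated postoperative way to find respiratory depression is to ask the patient at 1h; the protocol text gives no postoperative respiratory rate, SpO2, sedation score or cut-off

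*Combined protocol and SAP*

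**What the plan says.** Section 5, step 8, starts patient-controlled analgesia (PCA) straight after extubation in both arms, "equipped with 0.5mg/ml oxycodone, 1ml/h background infusion, 3ml additional infusion and locked for 5min".

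Step 9 covers the first hour: "The patients were observed in the PACU for one hour". It names no variable to be watched. At 1h it specifies VAS scores and spirometry, and then questioning: "Ask the patient if there are any adverse reactions, such as nausea, vomiting, itching, dizziness, headache, shoulder pain, respiratory depression, etc".

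Step 10 covers the ward visits at 2h, 4h, 8h and 24h, where "the dosage of PCA, the times of rescue analgesia, VAS scores at rest and cough and adverse reactions were recorded". It does not say how adverse reactions are to be looked for.

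Oxygen saturation is named before and during surgery. Step 3 has "Blood pressure, pulse, oxygen saturation and ECG were monitored", and step 6 lists SpO2 again during maintenance, with end-expiratory CO2.

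The Background (section 1) says that "with the increase of the dose of opioids, the adverse effects will become more pronounced, such as respiratory depression".

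Three other places bear on the point:
- Section 3.3: the patients and "an investigator who was responsible for follow-up during 48 postoperative hours were blinded to the randomization groups".
- Section 4.3, item 4, gives as a ground for exit: "Serious adverse events, complications or special physiological changes are not suitable for further study".
- Section 7.1 requires an Adverse Event Record Form and asks the investigator to explain the severity criteria. It states none for respiratory depression.

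**The concern.** Most items on the step 9 list, such as nausea, itching, dizziness and shoulder pain, are things a patient feels and can report. Respiratory depression is a sign that someone else has to observe. A patient sedated enough to have it is a poor witness to it. Following step 9 as written applies a method that suits the symptoms but not this item, and step 10 puts nothing in its place on the ward.

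The case for the trial rests partly on sparing opioid, and the Background uses respiratory depression as its example of opioid harm. Readers will therefore look for that count. If the report says that none occurred, they will not know what was measured, in how many patients, or what would have qualified. At stake is the meaning of one descriptive safety figure.

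**Working it through.** **1. What is specified at each time (section 5).**

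| Time | What the text names | Respiratory rate, SpO2 or sedation score |
|---|---|---|
| Before induction (step 3) | oxygen saturation, among others | SpO2 |
| Maintenance (step 6) | SpO2 and end-expiratory CO2, among others | SpO2 |
| 1h (step 9) | PACU observation, VAS, spirometry, questioning | none |
| 2h (step 10) | PCA dose, rescue count, VAS, adverse reactions | none |
| 4h (step 10) | as 2h, plus spirometry | none |
| 8h (step 10) | as 2h | none |
| 24h (step 10) | as 2h, plus spirometry and QoR-15 | none |

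Postoperative assessments with any of the three specified: 0 of 5. No definition or cut-off for respiratory depression appears in any section.

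**2. Opioid exposure allowed (step 8).** Background: 0.5 mg/ml × 1 ml/h = 0.5 mg/h, or 0.5 × 24 = 12 mg over 24 hours. Bolus: 0.5 mg/ml × 3 ml = 1.5 mg. A 5-minute lockout allows 60/5 = 12 boluses an hour, and no hourly maximum is stated. The ceiling is therefore 12 × 1.5 + 0.5 = 18.5 mg/h. That is what the settings permit, not expected use; the pilot means in section 3.2 were 23.7 and 28.7 mg of morphine over a whole day. Step 9 also allows a 2 mg oxycodone rescue dose in the PACU.

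**3. Do other provisions fill the gap?** Section 7.1 says what to write down about an event, and section 4.3, item 4, says what may follow from one. Both begin once an episode has been noticed; neither says how to look. Spirometry is a separate outcome (6.2, item 4), is taken at three of the five assessments, needs a cooperating patient, and is not tied to respiratory depression.

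**4. Direction of the error.** If only noticed episodes are counted, the count can be too low. The stated procedure is the same in both arms and the follow-up investigator is blinded, so nothing in the text makes detection better in one arm. How many episodes would go unnoticed cannot be derived from the documents.

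**5. What a measured count would support.** Section 3.2 gives 41 per group and a 10% dropout allowance: 41/0.9 = 45.6, rounded up to 46 per group, 92 in total, as stated. If no patient met the cut-off, the exact two-sided 95% upper limit would be 1 − 0.025^(1/n):
- n = 92: 1 − 0.025^(1/92) = 3.9%
- n = 82 (2 × 41): 1 − 0.025^(1/82) = 4.4%

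These limits apply to respiratory depression visible at the visits, not to all episodes in 24 hours. They need a known number measured and a stated definition, and the present text supplies neither.

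**The case against.** The strongest reply is that little follows from the gap. Respiratory depression is not a named outcome; it enters the secondary outcomes only by inference, under postoperative complications (6.2, item 6). The other reactions on the list have no definitions either. Patients are extubated awake, give VAS scores at every visit, and sit up for spirometry at 1h, 4h and 24h. One too sedated to answer would often be noticed face to face. The record form is not in the documents and may already contain the fields, and PACU care may well include SpO2.

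Much of this stands, and it keeps the point minor. It does not close the gap. Face-to-face contact supplies no definition and no recorded value, and routine care that the protocol does not ask to be recorded is not trial data. Respiratory depression also differs from the rest of the list in being a sign, and it is the example of harm that the Background chooses.

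Three stronger readings are tempting, and the documents support none of them:
- **Patients are unmonitored after surgery.** The text is silent on the variables. Silence does not show that nothing was watched.
- **The comparison between arms is biased.** Follow-up is blinded and the procedure is common to both arms.
- **The stopping rule in 7.3 is undermined.** That rule concerns mortality and complications overall and names no test, so its behaviour cannot be judged from this one event type.

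**Conclusion.** The point holds as a minor one. After surgery, the only stated method for finding respiratory depression is a question to the patient at 1h, and the text specifies no relevant measurement at any of the five assessments. A descriptive count could be too low in both arms, by an amount the documents do not allow one to estimate. No differential bias is shown, and neither the primary outcome nor the sample size is affected.

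The conclusion rests on the protocol text. If the Adverse Event Record Form already calls for respiratory rate and SpO2 with a definition, what remains is to say so in steps 9 and 10.

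**What to change.** In steps 9 and 10, have the blinded follow-up investigator record respiratory rate and SpO2 at the existing 1h, 2h, 4h, 8h and 24h visits. Take them before VAS or spirometry, so that rousing, coughing and forced breathing do not alter the reading. A brief score on one named sedation scale is optional.

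Define respiratory depression in advance by a numeric cut-off. Respiratory rate below 10/min or SpO2 below 90% would serve as a starting point; these values are assumptions, not taken from the documents, and the sponsor should confirm or replace them. Report the count descriptively by arm, with the number of patients measured. Keep questioning for the symptoms patients can feel, but stop relying on it alone for this item.

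The cost is two form fields, or three with the sedation score, and about a minute per visit (assumed), so roughly five minutes per patient. No new visits are needed. The remaining weakness is that spot checks miss what happens between them, above all in the 16 hours from 8h to 24h, so the result should be described as respiratory depression seen at visits.
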